2.0 Rational and Specific Aims

Both of the pain control modalities in this study have been used as postoperative analgesia in prior studies. The specific aim of this study is to compare the difference between the pain control methods in achieving the following:

1. Decreased opioid requirements
2. Improved postoperative pain scores
3. Decreased opioid side effects (Nausea, sedation, ileus, urinary retention, respiratory depression)

The primary endpoint of this study will be VAS pain score. The VAS scores will be taken with both rest and movement.

The secondary endpoint includes intravenous opioid consumption and opioid side effects (nausea, sedation, ileus, urinary retention, respiratory depression). The IV and PO opioid doses will be quantified at 1, 24, and 48 hours. We will also measure postoperative nausea and sedation scores at 1, 24 and 48 hours. We will also assess patient satisfaction postoperative at 24 and 48 hours. We will also measure time to first flatus, incidence of urinary retention, incidence of respiratory depression, ambulation activity, and hospital length of stay.

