All patients will receive PO acetaminophen and PO gabapentin the morning of surgery. Pt. will be placed on PRN oxycodone/acetaminophen (Percocet) postoperatively. PRN IV dilaudid may be given for severe breakthrough pain.

Opioid usage at 1, 24 and 48 hours after the block will be recorded by a member of the research team. Pain scores at rest and on movement will be measured by the investigator using Visual Analog Scale (VAS). Nausea will be measured using a categorical scoring system (none=0; mild=1; moderate=2; severe=3). Sedation scores will also be assessed by a member of the study team using a sedation scale (awake and alert=0; quietly awake=1; asleep but easily roused=2; deep sleep=3). All these parameters will be measured at 1, 24 and 48 hours after the blocks and patients will be encouraged to ambulate on postoperative day 1 under supervision. Their ambulation activity will be recorded.

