8.0 Statistical consideration

Primary outcome: VAS score at 24 and 48 hours

Primary Research Hypothesis: ESP block will provide lower postoperative pain scores compared to TAP block for laparoscopic hysterectomy as measured by VAS scores at 24 and 48 hours

Secondary outcomes: Narcotic usage after 1, 24 and 48 hours. Pain scores using VAS at rest and walking at 1, 24 and 48 hours. Nausea scores at 1, 24 and 48 hours. Sedation scores at 1, 24 and 48 hours. If the patient is discharged within 48 hours, every effort will be made to obtain data points. We will also assess patient satisfaction postoperative at 24 and 48 hours. We will also measure time to first flatus, incidence of urinary retention, incidence of respiratory depression, ambulation activity and hospital length of stay.

Secondary Research Hypotheses: ESP block will show improved patient satisfaction scores and decreased nausea and sedation scores compared to TAP block.

Statistical analysis will be performed using a standard statistical program (SAS or SPSS). All data will be summarized (means, standard deviations, standard errors, and ranges for continuous variables; frequencies and percentages for categorical variables) by group. Demographic data will be compared between the four groups using ANOVA or chi-square tests as appropriate. The primary outcome, VAS at 24 and 48 hours, will be compared between the groups using repeated measures ANOVA; the model will include fixed effects for group, time, and the group by time interaction and random effects to allow correlations between the two times and different variances for the two times. Pain and satisfaction scores and opioid usage over time will be analyzed using repeated measures ANOVA. Nausea and sedation scores will be compared between groups at each time point using Mantel-Haenszel chi-square tests for ordered categorical data. Time to first flatus will be compared using log-rank survival analysis; incidence of urinary retention, incidence of respiratory depression, and ambulation activity will be compared using chi-square tests; and hospital length of stay will be compared using Wilcoxon Rank Sum tests. Distributions of the continuous variables will be examined, and a transformation of the data (e.g. natural logarithm) or nonparametric tests will be used as necessary. A 5% significance level will

be used for all comparisons.

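### Nausea and sedation have no scheduled score between 1 and 24 h and no recall window, so these two Aim 3 components are likely to be under-captured

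*Combined protocol and SAP*

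**What the plan says.** Section 2.0 sets Aim 3 as "Decreased opioid side effects (Nausea, sedation, ileus, urinary retention, respiratory depression"). Two of those five effects, nausea and sedation, are to be scored at fixed hours: "We will also measure postoperative nausea and sedation scores at 1, 24 and 48 hours". Section 5.0 counts those hours from the block and applies them to pain as well: "All these parameters will be measured at 1, 24 and 48 hours after the blocks".

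The scales are also in Section 5.0. Nausea: "Nausea will be measured using a categorical scoring system (none=0; mild=1; moderate=2; severe=3"). Sedation: "sedation scale (awake and alert=0; quietly awake=1; asleep but easily roused=2; deep sleep=3"). Neither comes with a recall period.

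The secondary hypothesis in Section 8.0 is that "ESP block will show improved patient satisfaction scores and decreased nausea and sedation scores compared to TAP block". The analysis is by time point: "Nausea and sedation scores will be compared between groups at each time point using Mantel-Haenszel chi-square tests for ordered categorical data".

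The other Aim 3 effects are collected differently. Section 2.0 says: "We will also measure time to first flatus, incidence of urinary retention, incidence of respiratory depression, ambulation activity, and hospital length of stay". Section 8.0 analyses time to first flatus by log-rank, and urinary retention and respiratory depression as incidences by chi-square.

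**The concern.** Nausea and sedation from opioids tend to come and go. A score of the patient's state at 24 h cannot separate someone who was severely nauseated on the evening of surgery and recovered from someone who was never nauseated: both score 0. The interval without a score lasts 23 h and covers most of the first day, when patients have as-needed oral and intravenous opioids available (Section 5.0).

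Nothing else in the plan fills this gap for nausea or sedation. Section 6.0 has the primary team report adverse events, but it provides no graded nausea score and no record of vomiting or antiemetic use.

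What is at stake is how a null result would be read. If the nausea comparison shows no difference, the reader cannot tell whether the blocks are alike or the episodes fell between readings. The lost information cannot be recovered once the data are in. Pain has the same gap, but the primary outcome is defined as VAS at 24 and 48 h and is measured as defined.

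**Working it through.** **The plan's own figure.** The only power statement (Section 8.0) concerns VAS: coefficient of variation 0.70, ratio of means 1.6, 40 per group, two-sided 5%, 90% power. On the log scale, SD = sqrt(ln(1 + 0.70²)) = 0.6315 and the difference is ln(1.6) = 0.4700. Power is 0.914 (normal) or 0.908 (t, 78 df), so the stated 90% reproduces. It has no bearing on nausea or sedation, for which the plan gives no power.

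**How each Aim 3 component is captured.**

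| Component | Measure | Depends on the 1, 24 and 48 h scores? |
|---|---|---|
| Nausea | 0-3 score, tested at each time | Yes |
| Sedation | 0-3 score, tested at each time | Yes |
| Ileus | Time to first flatus, log-rank | No |
| Urinary retention | Incidence, chi-square | No |
| Respiratory depression | Incidence, chi-square | No |

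So 2 of 5 components are exposed.

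**How much a current-state reading could miss.** The documents give no incidence or duration, so everything in this step except the 40 per group and the two-sided 5% level is assumed:
- each affected patient has one episode of length L, starting at a random time between 1 and 24 h (23 h);
- the score records the present state;
- the test is a binary chi-square, nausea present or absent.

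The chance that the episode is still present at the 24 h reading is L/23. The expected prevalence at 24 h is the true incidence × L/23. For example, with L = 4 h, 50% × 4/23 = 8.7% and 25% × 4/23 = 4.3%. Power comes from exact enumeration of all outcomes with 40 per group.

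| L | L/23 | 50% v 25% becomes | Power | 50% v 20% becomes | Power |
|---|---|---|---|---|---|
| 2 h | 9% | 4.3% v 2.2% | 4% | 4.3% v 1.7% | 5% |
| 4 h | 17% | 8.7% v 4.3% | 13% | 8.7% v 3.5% | 16% |
| 8 h | 35% | 17.4% v 8.7% | 22% | 17.4% v 7.0% | 32% |
| 12 h | 52% | 26.1% v 13.0% | 32% | 26.1% v 10.4% | 45% |
| 16 h | 70% | 34.8% v 17.4% | 43% | 34.8% v 13.9% | 60% |
| Any nausea since last assessment | – | 50% v 25% | 65% | 50% v 20% | 82% |

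In the top row the expected counts are 40 × 4.3% = 1.7 and 40 × 2.2% = 0.9 patients. With so few events the test is conservative, which is why power falls below the nominal 5%.

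The direction is the same in every row: the single reading is less powerful than the period measure, and the loss shrinks as episodes lengthen.

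**The case against.** The strongest reply is that the plan never says the scores describe the present moment. A none-to-severe nausea scale could be completed as the worst since the last contact, and the secondary hypothesis speaks of scores, which the plan does compare as stated. For nausea this stands in part: current state is the more natural reading of a score measured at an hour, but it is an inference. It does not remove the problem, because assessors could apply either meaning. It does not help sedation, where levels such as quietly awake or deep sleep describe what an observer sees at the time.

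A second reply is that the size rests on chosen inputs. That also stands. The illustration assumes one episode per patient, ignores the 1 h reading, and uses a binary test where the plan uses an ordinal one. Longer episodes narrow the gap. Even the period measure has only about 65% power for a halving from 50%, so it would miss that effect about one time in three.

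A reader might go further and infer that the whole interval from 1 to 24 h is unobserved, or that Aim 3 cannot be answered. The documents do not support either. Opioid usage is recorded as an amount, flatus as a time to event, retention and respiratory depression as incidences, and adverse events are reported throughout. Nor does Aim 2 make any specific claim about first-evening pain.

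The time origin is a related matter. Hours run from the block, which is placed before surgery for ESP and after induction for TAP (Section 5.0), so the 1 h reading may fall during surgery. That bears on what the 1 h score can contribute, but the gap from 1 to 24 h is there regardless.

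**Conclusion.** The point holds for nausea and sedation: no scheduled score between 1 and 24 h, no stated recall window, and no analysis over a period. Read as current-state scores, they would miss many first-day episodes. Two of the five Aim 3 components, and the matching part of the secondary hypothesis, are under-captured rather than unanswerable.

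The extent of the loss cannot be derived from the documents. The range of about 4% to 43% power against about 65% shows how large it could be under the stated assumptions. It should not be quoted as an estimate for this trial, nor taken to mean that the plan is bound to report no difference.

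The primary outcome is untouched, and so are the other three side effects and opioid usage. This is a worthwhile improvement to secondary outcomes, not a flaw in the main comparison.

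**What to change.** In Sections 5.0 and 8.0, using the 24 and 48 h contacts already planned:

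- Record worst nausea since the previous assessment on the same 0-3 scale, and any vomiting or antiemetic given, taken from the chart.
- Make worst nausea over 0-24 h and over 24-48 h the nausea outcome for the secondary hypothesis, with the same Mantel-Haenszel test. For 0-24 h, take the higher of the 1 h score and the worst-since score recorded at 24 h.
- Label the existing point scores as current state and keep them as descriptive.
- State that sedation readings describe only the moments assessed and will not support a claim about sedation over the postoperative period.
- Optionally, add worst pain since the previous assessment, at rest and on movement, as a descriptive secondary item. Leave the primary VAS at 24 and 48 h unchanged.

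The cost is a few questions and a chart check at existing contacts, plus a short change to the analysis text, with no extra visit or procedure. The downside is some recall error over 24 h. Since patients and assessors are planned to be blinded (Section 4.0), there is no evident reason for that error to favour one arm. The change has to be in place before data are collected, because missed episodes cannot be reconstructed reliably afterwards.

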6.0 Reporting of Adverse Events

Patients will be monitored by the primary team during the postoperative period, and any adverse events or unanticipated problems such as local anesthetic toxicity or any abdominal injury will be reported to the acute pain service and research team. All adverse events or unanticipated

problems that meet the criteria for prompt reporting will be reported to the IRB within 5 business days.

7.0 Study withdrawal/DC

The patient can withdraw from the study at any time by contacting the research team or acute pain anesthesia resident. In such an event, patient may still have access to all the IV and oral pain medications. Anesthesia acute pain team will continue to follow the patient for 24 hours. After 24 hours, the anesthesia acute pain team will sign off and all further pain management will be done by the primary team.

8.0 Statistical consideration

Primary outcome: VAS score at 24 and 48 hours

Primary Research Hypothesis: ESP block will provide lower postoperative pain scores compared to TAP block for laparoscopic hysterectomy as measured by VAS scores at 24 and 48 hours

Secondary outcomes: Narcotic usage after 1, 24 and 48 hours. Pain scores using VAS at rest and walking at 1, 24 and 48 hours. Nausea scores at 1, 24 and 48 hours. Sedation scores at 1, 24 and 48 hours. If the patient is discharged within 48 hours, every effort will be made to obtain data points. We will also assess patient satisfaction postoperative at 24 and 48 hours. We will also measure time to first flatus, incidence of urinary retention, incidence of respiratory depression, ambulation activity and hospital length of stay.

Secondary Research Hypotheses: ESP block will show improved patient satisfaction scores and decreased nausea and sedation scores compared to TAP block.

Statistical analysis will be performed using a standard statistical program (SAS or SPSS). All data will be summarized (means, standard deviations, standard errors, and ranges for continuous variables; frequencies and percentages for categorical variables) by group. Demographic data will be compared between the four groups using ANOVA or chi-square tests as appropriate. The primary outcome, VAS at 24 and 48 hours, will be compared between the groups using repeated measures ANOVA; the model will include fixed effects for group, time, and the group by time interaction and random effects to allow correlations between the two times and different variances for the two times. Pain and satisfaction scores and opioid usage over time will be analyzed using repeated measures ANOVA. Nausea and sedation scores will be compared between groups at each time point using Mantel-Haenszel chi-square tests for ordered categorical data. Time to first flatus will be compared using log-rank survival analysis; incidence of urinary retention, incidence of respiratory depression, and ambulation activity will be compared using chi-square tests; and hospital length of stay will be compared using Wilcoxon Rank Sum tests. Distributions of the continuous variables will be examined, and a transformation of the data (e.g. natural logarithm) or nonparametric tests will be used as necessary. A 5% significance level will

be used for all comparisons.

Based on prior studies, the coefficient of variation for the VAS score at 24 and 48 hours is estimated to be 0.70. With a sample size of 40 per group the study will have 90% power to detect a ratio of means of 1.6 for VAS score between any two groups, assuming two-sided tests each conducted at a 5% significance level.

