1.0 Background

Each year, thousands of hysterectomies are performed for various indications including cancer, fibroids, endometriosis, and other conditions. Laparoscopic hysterectomy is often complicated by post-operative pain, making pain control challenging especially with the use of opioids. Improved pain control increases patient satisfaction and may lead to improved postoperative course.[1, 2] Our standard of practice at Indiana University Hospital is to perform Transverse Abdominis Plane (TAP) block using liposomal bupivacaine (LB) for these patients to help with postoperative analgesia. [3] Recent literature suggests that Erector Spinae Plane (ESP) block may be a safe and effective alternative for thoracic, extremity, and abdominal surgeries. [4] Currently there are numerous case reports supporting use of ESP block [5] but there are not prospective randomized controlled trials comparing these 2 blocks to date. . Our study aims to compare the efficacy of ESP block and TAP block in laparoscopic hysterectomy.

The ESP block, first described by Forero in 2016, provides regional anesthesia targeting in the range of the T2-L1 branches of thoracolumbar nerves.[6] The ultrasound is positioned in a parasagittal fashion, lateral to the spinous process, to visualize the transverse process. The needle is inserted cranial-to-caudal in plane traversing through the trapezius muscle, the rhomboid major muscle, and the erector spinae muscles, aiming to make contact with the transverse process, with the needle tip deep to the plane of the erector spinae muscle, which overlies the transverse process. Injection of saline confirms the correct location of the needle as determined by cranio-caudal spread of saline under the erector spinae muscle, “lifting” it off of the transverse process. Once the correct location is identified, the local anesthetic is injected.

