3.0 Inclusion/Exclusion

Inclusion criteria:

- Patients undergoing laparoscopic hysterectomy surgery at Indiana University Hospital
- ASA class 1, 2, 3 or 4
- Age 18 or older, female
- Desires Regional anesthesia for postoperative pain control

Exclusion criteria:

- Any contraindication for ESP or TAP block.
- History of substance abuse in the past 6 months.
- Patients on more than 30 mg morphine equivalents of opioids.
- Any physical, mental or medical conditions which in the opinion of the investigators, may confound quantifying postoperative pain resulting from surgery.
- Known allergy or other contraindications to the study medications (Acetaminophen, Gabapentin, Bupivacaine).
- Postoperative intubation.
- Any BMI greater than 40.0.

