4.0 Enrollment/Randomization

All laparoscopic hysterectomy cases scheduled by OBGYN at IU Health University Hospital will be identified. Subjects will be contacted face-to-face prior to surgery. They will be informed about the study and all questions will be answered. All patients will undergo a standardized enhanced recovery perioperative care pathway designed and agreed upon by the perioperative team of anesthesiologists and surgeons.

A total of 80 subjects will be randomized by a computer program into two groups (40 in each group):

1. TAP block – placed by ultrasound using 266mg Exparel (20ml) and 60ml of 0.125% bupivacaine. 40ml on each side. 20ml injected for subcostal TAP and 20ml injected for posterior TAP.

2. ESP block – placed by ultrasound using 266mg Exparel (20ml) and 60ml of 0.125% bupivacaine. 40ml on each side. 20ml injected at T8 and 20ml injected at T12

Randomization will be performed using a block randomization of the 2 groups instead of a simple 2-group randomization to keep the study groups fairly balanced throughout enrollment. The primary investigator will inform the person doing the block as to what group the patients are randomized to. Both the patients and the research staff doing assessments will be blinded to the randomization.

5.0 Study procedures:

The TAP blocks will be placed intraoperatively after induction, while ESP blocks will be done preoperatively. All procedures will be done using sterile technique with masks, hats, and sterile gloves. All procedures will be placed under the supervision of the attending anesthesiologist on the acute pain service.

For the TAP block, the ultrasound probe is placed transverse to the abdominal wall, between the iliac crest and the costal margin. The needle is placed in the plane of the probe and advanced until it is between the internal oblique and the transversus abdominis muscles. Once in the plane, 2 mL of saline is injected to confirm needle position, then the local anesthetic solution is injected. [10]

For the ESP block, as mentioned previously, the ultrasound is positioned in a parasagittal fashion, 2-3 inches lateral to the spinous process. This approach visualizes the transverse process. The needle is inserted cranial-to-caudal to make contact with the shadow of the transverse process, with the needle tip deep to the fascial plane of the erector spinae muscle. Injection of saline confirms the location of the needle, and the anesthetic is injected.

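### The primary VAS model names no baseline covariate; prespecifying age and preoperative opioid use would be a cheap possible gain in precision, though the unadjusted analysis is valid and meets its stated power

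*Combined protocol and SAP*

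**What the plan says.** Section 8.0 defines the endpoint as "Primary outcome: VAS score at 24 and 48 hours". For the repeated-measures ANOVA it says that "the model will include fixed effects for group, time, and the group by time interaction", and it adds random effects so that the two times may be correlated and have different variances. No baseline term appears there, and no adjusted or sensitivity model appears elsewhere. Demographic data are only to be compared between groups.

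Two patient characteristics have to be looked at before entry. Section 3.0 sets a minimum age of 18, and its exclusions include "Patients on more than 30 mg morphine equivalents of opioids". Section 4.0 describes block randomisation with no stratification factor, and says "Subjects will be contacted face-to-face prior to surgery". Section 5.0 schedules VAS only at 1, 24 and 48 hours after the block, so no baseline score is planned.

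The sample size statement in Section 8.0 says that "the coefficient of variation for the VAS score at 24 and 48 hours is estimated to be 0.70" and claims "90% power to detect a ratio of means of 1.6 for VAS score between any two groups" with 40 per group, two-sided at 5%.

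**The concern.** The population is mixed: any adult age, ASA class 1 to 4, opioid use from none up to the limit and, according to Section 1.0, "hysterectomies are performed for various indications including cancer, fibroids, endometriosis, and other conditions". If some of these features predict pain at 24 and 48 hours, a model without them leaves that variation in the residual. With a coefficient of variation of 0.70 and 40 patients per arm, a smaller residual would help.

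In a randomised trial, adjusting for prespecified baseline values keeps the 5% error rate and can only usefully narrow the interval if the values are prognostic. Prespecification also matters for credibility. The plan compares demographics between groups but does not say what would follow if they differed, which leaves room for covariates to be chosen after the data are seen.

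**Working it through.** **Inputs from Section 8.0 and Section 4.0.** Coefficient of variation 0.70; ratio of means 1.6; 40 per group; two-sided 5%.

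**Step 1: reproduce the plan's figure, without covariates.** On the log scale:
- SD = sqrt(ln(1 + 0.70²)) = sqrt(ln 1.49) = 0.6315
- difference = ln(1.6) = 0.4700
- standardised difference = 0.4700 / 0.6315 = 0.744
- noncentrality = 0.744 × sqrt(40/2) = 3.33, with 78 degrees of freedom

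Power is 90.8% by the noncentral t distribution and 91.4% by the normal approximation. The normal approximation needs 38 per arm for 90%. The stated 90% with 40 per group is therefore reproduced with no adjustment.

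**Step 2: add covariates.** If baseline covariates explain a share R² of log-VAS variance within groups, the residual SD is 0.6315 × sqrt(1 − R²), and 40 per arm is worth 40 / (1 − R²) per arm. R² is not in the documents, so the values below are assumed. R² = 1% corresponds to a correlation of 0.1, and R² = 25% to a correlation of 0.5.

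| Assumed R² | Residual SD | Power at 40 per arm | Equivalent n per arm |
|---|---|---|---|
| 0 | 0.632 | 90.8% | 40.0 |
| 1% | 0.628 | 91.0% | 40.4 |
| 5% | 0.616 | 92.1% | 42.1 |
| 10% | 0.599 | 93.4% | 44.4 |
| 25% | 0.547 | 96.7% | 53.3 |

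**Step 3: price the degrees of freedom.** Deducting 3 degrees of freedom (75 in place of 78) changes each of these powers by less than 0.1 percentage point. Even at R² = 1%, the adjusted model does not lose power.

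**Limits of the calculation.** It treats one time point. In the planned two-time model the gain also depends on the correlation between the 24-hour and 48-hour scores, which the documents do not give.

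**The case against.** The strongest reply is that nothing here needs repair. The unadjusted model is valid under randomisation, chance imbalance is already covered by the standard error and the 5% level, and "With a sample size of 40 per group the study will have 90% power" is borne out. All of that stands.

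A reader might go further than the documents allow in four ways.

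- **That precision is certainly being lost.** No correlation between age or opioid use and VAS is given. At a correlation of 0.1 the gain is about 0.3 of a percentage point, and nothing in the text rules that out.
- **That the whole range is free.** A baseline VAS is the most plausible route to the upper end, and it would be a new measurement. Age and opioid use alone may explain little.
- **That opioid use is already a recorded variable.** Section 3.0 requires only a check against the 30 mg limit. Use at or below the limit may not be written down, and the exclusion cuts the range, which could weaken the variable as a predictor.
- **That adjustment is needed to rescue power.** On the untransformed scale with a constant coefficient of variation, power is about 81%. That method does not reproduce the plan's 90%, so I do not rest the point on it.

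What survives is narrower. Prespecified adjustment costs almost nothing, cannot do appreciable harm to power, and may help.

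**Conclusion.** The point holds as a possible efficiency gain, not as an error in the analysis or the sample size. The primary model omits baseline covariates, although age must be known for every patient and opioid use must be checked. Under assumed R² of 1% to 25%, the gain at 40 per arm runs from about 0.3 to 5.9 percentage points (90.8% to 91.0% at one end, allowing for rounding, and to 96.7% at the other). Where in that range the trial would fall cannot be said from the documents. The figures assume log-scale analysis, the plan's own variability and effect, full data on 40 per arm, and a single time point. The recommendation does not depend on the upper end, because the cost is close to nil even at the lower end.

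**What to change.** **In Section 8.0:** name age and preoperative opioid use (yes/no) as fixed covariates in the primary repeated-measures model, before any outcome data are seen by group. Keep the unadjusted model as a sensitivity analysis. For this to work, the study record must hold opioid use as yes/no at screening, and not only the result of the 30 mg check. The cost is one sentence in Section 8.0, one field on the screening form and 2 degrees of freedom.

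**As a separate, optional addition in Section 5.0:** record one VAS, at rest and on movement, at the face-to-face preoperative contact, and enter the score that matches the outcome being modelled as a further covariate. The timing must be the same in both arms and before allocation is acted on. A rule tied to the moment before the block would not do, because Section 5.0 places the ESP block preoperatively and the TAP block after induction. The cost is about a minute per patient and 1 more degree of freedom.
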